7.2.2. ALT Elevation

7.2.2.1. ALT Elevation without Declining Hepatic Function

A confirmed ALT elevation on treatment is defined as $ALT > 2 \times \text{Baseline}$ or on-treatment nadir and $\geq 10 \times \text{ULN(Covance)}$ at 2 consecutive visits.

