7.5 Follow-up Assessments

All subjects who complete treatment per protocol or prematurely discontinue treatment will enter a 24-week follow-up period during which they will have the following assessments performed at 4, 8, 12, and 24 weeks (± 5 days) after the last dose of ABI-H2158 or PBO unless otherwise stated:

- Measure body weight (24 Weeks post only)
- Vital signs (temperature, heart rate, respiration rate and blood pressure)
- Complete physical examination (24 Weeks post only)
- Symptom-directed physical examination (not at 24 Weeks post)
- 12-lead ECG (24 Weeks post only)
- Review concomitant medications
- Review AEs
- Assess drug accountability (for ETV)
- Study drug dispensation (for ETV, 4 Weeks post and 12 Weeks post only)
- Laboratory analyses (additional details are provided in the Laboratory Manual):
 - Safety Labs: Chemistry, hematology, coagulation, urinalysis (4 Weeks post, 12 Weeks post, and 24 Weeks post only), and urine pregnancy test (if positive on dipstick, serum pregnancy test should be performed [4 Weeks post only]).
 - Virology/Immunology: HBV DNA, HBV pgRNA, HBsAg, HBeAg, HBcrAg, HBsAb and HBeAb (24 Weeks post only) sample for HBV sequencing and HBV nucleic acids
 - PK Sample: Sample for ETV can be collected at the same time with other labs (4 Weeks post only)

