7.7 Premature Termination Visit

Should a subject prematurely discontinue treatment ([Section 7.9.1](#)) or discontinue from the study ([Section 7.9.2](#)), a Premature Termination visit should be scheduled. While the Investigator may include additional assessments and evaluations determined by the status of the individual subject, at the minimum, the following assessments should be performed as soon as feasibly possible:

- Vital signs (temperature, heart rate, respiration rate and blood pressure)
- Complete physical examination (excluding breast and genitalia unless indicated)
- 12-lead ECG
- Review concomitant medications
- Review AEs
- Review dosing diary and assess drug accountability (if applicable)
- Laboratory analyses (additional details are provided in the Laboratory Manual):
 - Safety Labs: Chemistry, hematology, coagulation, urinalysis, urine drug test, and urine pregnancy test (if positive on dipstick, serum pregnancy test should be performed).
 - Virology/Immunology: HBV DNA, HBV pgRNA, HBsAg, HBeAg, HBcrAg, HBsAb and HBeAb, sample for HBV sequencing and HBV nucleic acids
 - PK Samples: Samples can be collected at the same time with other labs. See [Section 7.8.8](#) for additional information.

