7.9.1 Discontinuation From Treatment

If an individual subject is not satisfactorily tolerating study drug treatment due to AEs in the judgment of the Investigator, then – in consultation with the Sponsor - the subject may discontinue treatment with ABI-H2158 or PBO. ETV may be continued at the discretion of the Investigator. A subject also has the

right to discontinue treatment with AHI-H2158 or PBO due to his/her wish. Discontinuation from treatment does not mean discontinuation from the study. Subjects who prematurely discontinue treatment should immediately undergo the assessments listed for the Premature Termination visit ([Section 7.7](#)) and then continue scheduled follow-up assessments.

If a subject is determined to have developed substitutions in HBV Cp gene sequences associated with viral resistance or blunted treatment response ([Section 7.11](#)), then they will discontinue treatment with ABI-H2158 or PBO. ETV may be continued at the discretion of the Investigator. Subjects who prematurely discontinue treatment should immediately undergo the assessments listed for the Premature Termination visit ([Section 7.7](#)) and then continue scheduled follow-up assessments.

In this study, subjects will be closely monitored for any evidence of worsening hepatic function. Procedures to be followed for these subjects are described in [Section 9.4](#). Study treatment will be discontinued in subjects with confirmed evidence of declining hepatic function during treatment, a Premature Termination visit ([Section 7.7](#)) will be completed and subjects will subsequently undergo the follow-up assessments described in [Section 7.5](#).

Any subjects negative by urine pregnancy test at Baseline (Day 1) who are subsequently found to be positive on serum pregnancy test should immediately discontinue treatment with ABI-H2158 or PBO. ETV may be continued if indicated based on Investigator judgment in accordance with local practice and the approved ETV package insert. These subjects may be replaced at the discretion of the Sponsor.

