9.4 Management of ALT Elevations

All subjects participating in the study will be closely monitored for ALT elevations and/or signs of potential decline in hepatic function (see [Figure 2](#)). Subjects experiencing ALT elevations $\geq 2 \times$ Baseline (Day 1) or on-treatment nadir and $> 2 \times$ ULN during study treatment or during post-treatment follow-up should be closely monitored with regular Unscheduled Visits every 1-2 weeks at the discretion of the Investigator. At these visits, the following laboratory tests will be performed: ALT, AST, total bilirubin (if total bilirubin is elevated, reflex to direct bilirubin), serum albumin, INR and creatine kinase. The Investigator will determine if other Unscheduled Visit assessments should be performed. Additionally, the following guidance is provided for management of subjects with ALT elevations:

- ALT Elevation without Declining Hepatic Function
 - All subjects with an ALT elevation on treatment, defined as ALT $> 2 \times$ Baseline or on-treatment nadir and $\geq 10 \times$ ULN, should have the ALT findings confirmed within 3 days of receipt of the original results. All subjects should return for an Unscheduled Visit ([Section 7.6](#)).
 - If the ALT elevation is confirmed, then an additional Unscheduled Visit will be performed to further evaluate the subject. At this visit, the following laboratory tests will be performed: ALT, AST, total bilirubin (if total bilirubin is elevated, reflex to direct bilirubin), serum

albumin, INR, creatine kinase, HBV DNA, quantitative HBV serologies (HBeAg [reflex qualitative HBeAg if quantitative HBeAg is negative] and HBsAg [reflex qualitative HBsAg if quantitative HBsAg is negative]), HAV IgM, HCV RNA, HDV RNA, and HEV IgM. The Investigator will determine if other Unscheduled Visit assessments should be performed.

- If an intercurrent cause is determined to be causal, subjects with an ALT elevation without declining hepatic function and without contraindications may continue treatment and the intercurrent illness should be treated as deemed medically appropriate by the Investigator.
- Subjects with an ALT elevation without declining hepatic function and without contraindications may continue treatment with study drug under close observation.

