either resolved or resolving (defined as consistent ALT declines of 10% or more or normalization of ALT) on at least 2 successive visits.

If 2 or more subjects meet these ALT elevation management criteria, the US FDA and other relevant regulatory agencies will be notified, and subsequent steps will be determined after consultation with these agencies.

Following cessation of study drug treatment under this protocol, all subjects will be closely followed for ALT elevations and/or signs of potential decline in hepatic function. This applies to all subjects whether they prematurely discontinue study drug or complete the study treatment per protocol. Any subject with a post-treatment ALT elevation without evidence of declining hepatic function or a post-treatment ALT elevation with evidence of declining hepatic function as defined above, will be evaluated as noted above.

Figure 2: Management of ALT Elevation

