3.6.2. Analysis Visit Windows

Subject visits might not occur on protocol-specified days. Therefore, for the purpose of analysis, observations will be assigned to analysis windows. In general, the baseline value will be the last nonmissing value on or prior to the first dose date of study drug. The “on-treatment” period is defined up to the last dose date of ABI-H2158/PBO. The “off-treatment” period is defined after the last dose of ABI-H2158/PBO through the follow up period.

The assessment schedule is different in the Korea country specific protocol amendment. The analysis window will follow what is specified in the global protocol.

The analysis windows for on-treatment study assessments, including HBV DNA, HBV pgRNA, HBsAg, HBeAg, HBcrAg, adverse events, and clinical laboratories (chemistry, hematology, coagulation, urinalysis) are provided in [Table 3-1](#).

Table 3-1. On-Treatment Analysis Visit Windows for Study Assessments

Nominal Visit	On-Treatment Nominal Study Day	Visit Window Study Day	
		Lower Limit	Upper Limit
Day 1	1	(none)	1
Week 2	14	2	21
Week 4	28	22	42
Week 8	56	43	70
Week 12	84	71	98
Week 16	112	99	126
Week 20	140	127	154
Week 24	168	155	182
Week 28	196	183	210
Week 32	224	211	238
Week 36	252	239	266
Week 40	280	267	294
Week 44	308	295	322
Week 48	336	323	350
Week 52	364	351	378
Week 56	392	379	406
Week 60	420	407	434
Week 64	448	435	462
Week 68	476	463	490

Nominal Visit	On-Treatment Nominal Study Day	Visit Window Study Day	
		Lower Limit	Upper Limit
Week 72	504	491	≥504

The analysis windows for electrocardiograms (ECG) measurements are provided in [Table 3-2](#).

Table 3-2. On-Treatment Analysis Visit Windows for ECG

Nominal Visit	On-Treatment Nominal Study Day	Visit Window Study Day	
		Lower Limit	Upper Limit
Day 1	1	(none)	1
Week 12	84	2	126
Week 24	168	127	210
Week 36	252	211	294
Week 48	336	295	378
Week 60	420	379	462
Week 72	504	463	≥504

The analysis windows for off-treatment study assessments, including HBV DNA, HBV pgRNA, HBsAg, HBeAg, HBcrAg, vital signs, concomitant medications and adverse events, chemistry, hematology, coagulation and urinalysis are provided in [Table 3-3](#).

Table 3-3. Off-Treatment Analysis Visit Windows for Study Assessments

Nominal Visit	Off-Treatment Nominal Study Day	Visit Window Study Day	
		Lower Limit	Upper Limit
FU-Week 4	28	1	42
FU-Week 8	56	43	70
FU-Week 12	84	71	≥84

The analysis windows for ECG is provided in [Table 3-4](#).

Table 3-4. Off-Treatment Analysis Visit Windows for ECG

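### SAP 7.2.2.1 gives no confirmed by-arm count of isolated ALT elevations of at least 10 × ULN that are first seen (on a strict reading, also those only confirmed) after the last dose of ABI-H2158/PBO

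*Combined protocol and SAP*

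**What the plan says.** SAP 7.2.2.1 reads "A confirmed ALT elevation on treatment is defined as" ALT above 2 × Baseline or on-treatment nadir and at least 10 × ULN, at two consecutive visits. SAP 3.6.2 says that the on-treatment "period is defined up to the last dose date of ABI-H2158/PBO" and places everything later off-treatment.

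Protocol 9.4 words its own rule in the same way ("All subjects with an ALT elevation on treatment, defined as ALT") and asks for confirmation within 3 days of receiving the result: "All subjects should return for an Unscheduled Visit". It then goes beyond the treatment period. "Any subject with a post-treatment ALT elevation without evidence of declining hepatic function", or with such evidence, is to be evaluated under the same definitions.

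ALT is sampled off drug by design. Protocol 7.9.1 states: "Subjects who prematurely discontinue treatment should immediately undergo the assessments listed for the Premature Termination visit". Protocol 7.7 says that "a Premature Termination visit should be scheduled" for anyone who stops early. Protocol 7.5 times the follow-up visits "after the last dose of ABI-H2158 or PBO unless otherwise stated". SAP 1.2 keeps follow-up to 12 weeks after the early termination.

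The SAP's other safety periods are longer. TEAEs (7.1.5.1) and treatment-emergent graded laboratory abnormalities (7.2.1.1) run to last ABI-H2158/PBO dose + 28 days. Off-treatment summaries (7.1.6, 7.2.1.2) begin at day 29.

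**The concern.** SAP 1 records that development stopped because of ALT rises consistent with drug-induced liver injury, and safety is a primary objective. The confirmed count of large ALT elevations by arm is therefore one of the main safety results of the Synoptic CSR. When dosing stops because of a liver signal, a first or repeat sample may well be drawn off drug. A count that closes on the last dose date can miss such a subject, although neighbouring tables in the same report look further.

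The visit rule adds a smaller uncertainty. Neither 7.2.2.1 nor 7.2.2.2 says whether an Unscheduled Visit, where Protocol 9.4 takes the confirmatory sample, counts as a visit.

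**Working it through.** There is no planned figure to reproduce, since the sample size has no statistical basis (SAP 1.3). The check applies the definitions to test cases.

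**1. Samples outside the on-treatment period.** A subject who stops early has a Premature Termination draw and follow-up Weeks 4, 8 and 12: 1 + 3 = 4 draws, or 3 if the first falls on the last dose date. Whether subjects stopped by the sponsor had a separate Premature Termination draw may depend on the Clarification Letter, which is not among the documents.

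**2. Five hypothetical ALT courses.** Each has two successive samples above 2 × Baseline and at least 10 × ULN. Days are relative to the last ABI-H2158/PBO dose.

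| First, repeat | 7.2.2.1 as written (both by day 0) | Both by day +28 | First by day +28, repeat at any time | Grade 4 ALT table |
|---|---|---|---|---|
| −7, −4 | yes | yes | yes | treatment-emergent |
| 0, +3 | no (strict reading) | yes | yes | treatment-emergent |
| +4, +7 | no | yes | yes | treatment-emergent |
| +28, +31 | no | no | yes | both |
| +56, +59 | no | no | off-treatment row | off-treatment |

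As written, 1 of 5 is counted, or 2 of 5 if the second course is dated by its first sample. Extending the window to day +28 for both samples gives 3 of 5. Dating by the first sample gives 4 of 5, and the off-treatment row takes the fifth. All five appear in the Grade 4 tables. The courses were chosen to show how the rule works; they do not estimate a frequency.

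**3. Why a 28-day extension alone is not enough.** The follow-up Week 4 visit is allowed at 28 ± 5 = days 23 to 33, which is 11 days. Days 29 to 33, 5 of the 11, lie beyond last dose + 28. Weeks 8 and 12 lie wholly beyond it.

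**4. Visit rule.** Suppose last dose is study day 112. The first course then has samples on days 105 and 108, both inside the Week 16 analysis window (days 99 to 126, SAP Table 3-1). If a visit were programmed as an analysis window, even this course would supply only one visit. SAP 7.2.2 does not say that a visit means a window, but it does not exclude it.

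**5. Scale of one subject.** In a planned active arm, 1/30 = 3.3% (1/60 = 1.7% if cohorts are pooled). Exact 95% intervals: 0/30 gives 0 to 11.6%; 1/30 gives 0.1 to 17.2%.

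**6. Secondary point: grouping in 7.2.2.2.** The four laboratory limbs (ALT, direct bilirubin, albumin, INR) give 2⁴ = 16 patterns at one visit.
- ALT AND (bilirubin OR albumin OR INR): 8 patterns with ALT, less the 1 with no other limb = 7.
- (ALT AND bilirubin) OR albumin OR INR: 12 patterns with albumin or INR, plus 1 with only ALT and bilirubin = 13.
- The 13 − 6 = 7 shared patterns all include ALT. The 6 discordant patterns all lack a qualifying ALT elevation.

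**The case against.** The strongest reply is that the cut-off is imported from the visit-window section. SAP 7.2.2.1 does not cite 3.6.2, and the subsection just before it starts the off-treatment laboratory period at day 29, so on treatment could mean up to last dose + 28 days. That tension is real. But 3.6.2 is the SAP's only explicit definition of the on-treatment period, and on the day-29 reading later elevations still have no confirmed count by arm. The postbaseline wording in the counting paragraph of 7.2.2.2 might be read as widening 7.2.2.1, but that conflicts with the latter's explicit limit.

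Second, the raw information is already reported. ALT of at least 10 × ULN is Grade 4 (Protocol Appendix 2), tabulated by arm to day +28 and again from day 29, with all results listed. Because screening ALT above 5 × ULN is an exclusion, such a value is already at least 10/5 = 2 times any eligible screening value, although Day 1 may differ. This stands and limits the harm. What those tables lack is mainly confirmation.

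Third, the Protocol's post-treatment sentence is an instruction to evaluate subjects and does not require a table. That also stands: the SAP is out of step with the Protocol's scope but does not breach an analysis requirement.

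A reader might go further and infer that every confirmed ALT count omits post-dose events, or that the 7.2.2.2 composite cannot be determined. The documents support neither. SAP 7.2.2.2 carries no on-treatment limit and uses postbaseline values. Its two visit rules combine naturally, with components coinciding at a visit and the whole confirmed at the next. Its heading presupposes an ALT elevation, and the alternative grouping differs only where there is none. Symptoms are openly left out of the summary.

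**Conclusion.** The point holds in a limited form. Followed literally, the SAP gives no confirmed by-arm count for isolated ALT elevations of at least 10 × ULN first seen after last ABI-H2158/PBO dose. On a strict reading this extends to those confirmed only after that dose. It does not show that data are lost: unconfirmed values remain visible as Grade 4 ALT, and a post-dose rise with laboratory evidence of declining function can still enter 7.2.2.2.

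The number of subjects affected cannot be derived from the documents. The conclusion rests on reading on treatment in 7.2.2.1 as 3.6.2 defines it; a day-29 boundary narrows the gap without closing it. The change is worth making because the affected count bears directly on the reason for termination. The drafting of 7.2.2.2 is a secondary matter of wording.

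**What to change.** Analysis only:
- In SAP 7.2.2.1, count elevations whose first qualifying sample falls from first dose to last ABI-H2158/PBO dose + 28 days. Show later ones, under the same criteria, in a separate off-treatment row by arm.
- Define confirmation as the next available ALT sample by date, scheduled or unscheduled and regardless of drug status, using all records and not one record per analysis window.
- As a secondary wording point, state in 7.2.2.2 how the same-visit and two-consecutive-visit rules combine. Write out the AND/OR grouping after reconciling it with Protocol 9.4, which has the same ungrouped list. Which clinical grouping applies is not for this review to say.

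The cost is SAP wording and the reprogramming of one table and listing; the data are already collected. If the SAP is already final, SAP 1 provides for documenting later changes in the Synoptic CSR.

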7.2.2.2. ALT Elevation with Declining Hepatic Function

A confirmed ALT elevation with evidence of declining hepatic function is defined as meeting the following criteria at 2 consecutive visits:

- ALT elevation $\geq 2 \times \text{Baseline (Day 1)}$ or nadir and $> 2 \times \text{ULN(Covance)}$ AND
- Direct bilirubin increase to $\geq 2 \times \text{Baseline (Day 1)}$ and $\geq 2 \times \text{ULN(Covance)}$ OR
- Albumin decline $\geq 0.5 \text{ g/dL}$ OR $\text{INR} > 2 \times \text{Baseline (Day 1)}$ OR
- Symptoms of liver inflammation (eg, fatigue, weakness, lack of appetite, nausea, vomiting, jaundice or discolored feces)

The number and subjects meeting the above laboratory criteria will be summarized by treatment group. Clinical signs or symptoms of liver inflammation will not be included in the summary. For individual laboratory tests, subjects will be counted once based on the most severe postbaseline values. For the composite criteria, subjects will be counted once when the criteria are met at the same visit. The denominator is the number of subjects in the Safety Analysis Set who have nonmissing postbaseline values. A listing of subjects who met at least 1 of the above criteria will be provided.

7.3. Vital Signs

Descriptive statistics will be provided by treatment group for vital signs including heart rate, respiration rate, blood pressure, and body temperature as follows:

- Baseline value
- Values at each postbaseline time visit

- Change from Baseline at each postbaseline visit

A baseline value will be defined as the last available value collected on or prior to the date/time of first dose of study drug. Change from Baseline to a postbaseline visit will be calculated for any postbaseline visit.

In the case of multiple values in an analysis window, data will be selected for analysis as described in Section 3.6.3.

A by-subject listing of vital signs (systolic and diastolic blood pressure [mmHg], respiration rate [breaths/min], heart rate [bpm] and body temperature) will be provided by subject ID number and visit in chronological order.

7.4. Prior and Concomitant Medications

Medications collected at screening and during the study will be coded using WHODrug-Global-B3 v202003 of the World Health Organization (WHO) Drug dictionary.

7.4.1. Prior Medications

Prior medications are defined as any medications taken before a subject took the first dose of study drug.

Prior medications will be summarized by Anatomical Therapeutic Chemical (ATC) drug class Level 2 and preferred name using the number and percentage of subjects for each treatment group and overall. A subject reporting the same medication more than once will be counted only once within each ATC drug class. The summary will be ordered alphabetically by ATC medical class and then by preferred term in order of descending overall frequency within each ATC medical class. For drugs with the same frequency, sorting will be done alphabetically.

A medication will be considered as a prior medication if it meets one the following criteria:

- A medication with a start date prior to the first dose date of study drug will be included in the prior medication summary regardless of when the stop date is.
- If a partial start date is entered, the medication will be considered prior unless the month and year (if day is missing) or year (if day and month are missing) of the start date are after the first dose date of study drug.
- A medication with a completely missing start date will be included in the prior medication summary, unless otherwise specified.

Summaries will be based on the Safety Analysis Set.

7.4.2. Concomitant Medications

Concomitant medications are defined as medications taken while a subject was taking study drug. Use of concomitant medications will be summarized by ATC drug class Level 2 and preferred name using the number and percentage of subjects for each treatment group. A subject reporting the same medication more than once within each ATC drug class will be counted only once when calculating the number and percentage of subjects who received that medication. Medications may appear under multiple ATC drug classes. The summary will be ordered alphabetically by ATC medical class and then by preferred term in descending overall frequency within each ATC medical class. For drugs with the same frequency, sorting will be done alphabetically.

A medication will be considered as a concomitant medication if it meets one the following criteria:

- A medication with a start date prior to or on the first dose date of study drug, and continued to be taken after the first dose date.
- A medication started after the first dose date but prior to or on the last dose date of study drug.
- If a partial start date is entered, any medication with the month and year (if day is missing) or year (if day and month are missing) before study drug stop date and the stop date after the first dose date of study drug. If a partial stop date is entered, any medication with the month and year (if day is missing) or year (if day and month are missing) after the first dose date of study drug
- A medication started and stopped on the same day as the first dose date or the last dose date of study drug
- Medications with completely missing start and stop dates, unless otherwise specified.

A medications with a stop date prior to the date of first dose date of study drug or a start date after the last dose date of study drug will be excluded from the summary.

Summaries will be based on the Safety Analysis Set.

All prior and concomitant medications (other than per-protocol study drugs) will be provided in a by-subject listing sorted by subject ID number and administration date in chronological order.

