7.1.5.2. Incomplete Dates

If the onset date of the AE is incomplete and the AE stop date is not prior to the first dose date of study drug, then the month and year (or year alone if month is not recorded) of onset determine whether an AE is treatment emergent. The event is considered treatment emergent if both of the following 2 criteria are met:

- The AE onset is in the same or after the month and year (or year) of the first dose date of study drug, and
- The AE onset date is the same as or before the month and year (or year) of the date corresponding to 28 days after the date of the last dose of ABI-H2158/PBO

An AE with completely missing onset and stop dates, or with the onset date missing and a stop date later than the first dose date of study drug, will be considered to be treatment emergent. In addition, an AE with the onset date missing and incomplete stop date with the same or later month and year (or year alone if month is not recorded) as the first dose date of study drug will be considered treatment emergent.

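### SAP 7.4.2 leaves some medicines certainly taken on study drug out of the concomitant-medication table: mainly year-only starts in the year dosing ended, and missing starts, each with a complete on-treatment stop date

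*Combined protocol and SAP*

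**What the plan says.** SAP 7.4.2 gives a general definition: "Concomitant medications are defined as medications taken while a subject was taking study drug". It then sets the working test: "A medication will be considered as a concomitant medication if it meets one the following criteria". Three of the criteria deal with incomplete dates:

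- **Partial start.** The known part must come "before study drug stop date and the stop date after the first dose date of study drug".
- **Partial stop.** The known part must be after the first dose date. No condition is placed on the start date.
- **Missing dates.** "Medications with completely missing start and stop dates, unless otherwise specified".

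The section closes by excluding medicines stopped before first dose or started after last dose. It also promises a by-subject listing of all prior and concomitant medicines.

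Two neighbouring sections treat incomplete dates differently. SAP 7.1.5.2 (adverse events) is inclusive at both ends; the lower bound reads "The AE onset is in the same or after the month and year (or year) of the first dose date of study drug". It also has a rule for a missing onset with a later stop date. SAP 7.4.1 (prior medications) states: "A medication with a completely missing start date will be included in the prior medication summary, unless otherwise specified".

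**The concern.** The criteria are meant to put the definition into practice, yet some records that satisfy the definition fail them. The missing-date case is the odder one. A medicine with no dates at all is counted, while one whose stop date proves use during dosing has no rule.

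The year-level boundary is likely to matter in this trial. Development was stopped on 1 September 2021 (SAP 1), and subjects were to stay on ETV through 12 weeks of follow-up (SAP 1.2). The last dose of study drug is the later of the ABI-H2158/placebo and ETV dates (SAP 3.6.1). For subjects on treatment at termination, study drug therefore plausibly ended in 2021 (an inference), so a year-only start of 2021 sits on the boundary.

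What is at stake is how complete one by-arm table is. A reader may look at that table because development ended after ALT elevations, and because protocol 2.2.3.3 reports that itraconazole, rifampin and esomeprazole changed ABI-H2158 exposure markedly.

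**Working it through.** The plan states no figure to reproduce, so the check applies the rules literally and then counts date patterns.

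**Inputs.** The five criteria and the closing exclusion come from SAP 7.4.2, and the first and last dose definitions from SAP 3.6.1. Dosing dates are assumptions: A = 15 Jan 2021 to 10 Sep 2021; B = 15 Oct 2020 to 1 Dec 2021. Medicine dates run from Jan 2020 to Mar 2022.

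**Step 1: single records under A**

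1. Start 2021 (year only), stop 1 May 2021. 2021 < 2021 is false, so the partial-start test fails. The medicine was in use on 1 May, during dosing.
2. Start missing, stop 1 May 2021. There is no partial start or partial stop, and not both dates are missing. No explicit criterion applies.
3. Start missing or 2021, stop Jun 2021 (day missing). Jun 2021 is after Jan 2021, so the partial-stop rule counts it.
4. Both dates missing. Counted.
5. Start 2020, stop Jan 2021 (day missing). Jan 2021 is not after Jan 2021, so it is not counted. The true stop could be 1–14 Jan (before dosing) or 15–31 Jan, so it is only possibly concomitant.

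**Step 2: all patterns.** A pattern is certain if latest possible start ≤ last dose and earliest possible stop ≥ first dose.

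| Recorded start / stop | A: certain | A: no criterion met | B: certain | B: no criterion met |
|---|---|---|---|---|
| missing / complete | 239 | 239 | 413 | 413 |
| year only / complete | 680 | 240 | 868 | 336 |
| month-year / complete | 8084 | 23 | 9674 | 11 |
| month-year / year only | 27 | 7 | 48 | 2 |
| month-year / missing | 7 | 7 | 13 | 13 |
| missing / month-year | 7 | 0 | 13 | 0 |
| year only / month-year | 21 | 0 | 28 | 0 |

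Where the losses come from:

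- *Missing / complete:* one pattern per dosing day. A: 17+28+31+30+31+30+31+31+10 = 239. B: 78 days in 2020 + 335 in 2021 = 413.
- *Year only / complete:* A: 239 (start 2021, stop during dosing) + 1 (start 2020, stop on the first-dose day) = 240, and 240/680 = 35%. B: 335 + 1 = 336, and 336/868 = 39%. All but one in each case come from the strict *before*.
- *Month-year / complete:* A: 10 (start Sep 2021, stop 1–10 Sep) + 13 (stop on the first-dose day) = 23, or 0.3%. B: 1 + 10 = 11, or 0.1%.
- *Month-year / year only:* the start month is after the first-dose month and the stop year equals the first-dose year. These are exceptions to the remark under record 5: use is certain, but the strict *after* rejects them.
- *Month-year / missing:* a partial start with no stop recorded has no stop date to compare with first dose.

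**Step 3: after the change.** With inclusive comparisons, and a missing start counted when the stop is on or after first dose, the first four rows fall to 0 in both scenarios. The fifth row stays at 7 and 13 unless an ongoing or missing stop is also treated as continuing. It then falls to 0, because each of those starts lies within dosing.

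**Step 4: where the lost records still appear.** All are in the listing. Under SAP 7.4.1, missing starts are always prior medicines, and so is a year-only start in the first-dose year (record 1). A partial start in a later month or year than first dose is not prior. For example, start 2021 under B, or start Sep 2021 with stop 5 Sep 2021 under A, appears in the listing only.

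**The case against.** The best defence is that the general definition governs. Records 1 and 2 fall under neither closing exclusion. Any true start consistent with the 1 May stop means the medicine was either begun by first dose and continued, or begun during dosing, and both situations are listed criteria. A programmer could reason this way, or impute 1 January for a year-only start. But the SAP states neither step, and it gives partial starts their own rule, which record 1 fails. Two programmers could produce different tables from the same text.

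A second point stands in part. Because ETV continues into follow-up, the month-level boundary usually falls at the end of ETV, away from ABI-H2158 exposure, and the month-level losses are tiny. Year-only starts remain affected.

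A reader might also infer more than the text supports:

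- *That every year-only or missing start is lost.* No: the partial-stop rule rescues those with a partial stop after the first-dose month or year (record 3).
- *That the rule errs in one direction only.* No: a medicine with both dates missing is always counted, even if it was used only before or after dosing.
- *That chronic, herbal or over-the-counter products suffer most.* Nothing shows this. A long-standing medicine with an early start year passes the strict *before*, and protocol 6.4 requires start and stop dates to be recorded.
- *That the assessment of the ALT signal is compromised.* SAP 7.2.2 defines ALT elevations without using concomitant medication.

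**Conclusion.** The point holds as a minor drafting defect. Read literally, SAP 7.4.2 fails to count two kinds of medicine certainly taken on study drug: partial starts in the year (rarely, the month) that study drug stopped, and completely missing starts, in each case with a complete stop date during dosing. A partial stop in the first-dose month or year is, with the narrow exceptions shown, only possibly concomitant and does not support a claim of certain loss.

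The result is an undercount of these records, of unknown size, in one descriptive by-arm table. The percentages above are shares of possible date patterns under assumed dosing dates and do not predict how many subjects are affected. The listing keeps every record, and the prior-medication table keeps the missing starts and the year-only starts in the first-dose year. No efficacy, adverse-event or ALT analysis uses this classification.

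**What to change.** Align SAP 7.4.2 with SAP 7.1.5.2:

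- Partial start: count if its month/year (or year) is the same as or before that of the study-drug stop.
- Partial stop: count if its month/year (or year) is the same as or after that of first dose.
- Apply the same on-or-after test where a partial start is paired with a complete stop date.
- Completely missing start: count when the stop is on or after first dose.
- Ongoing or missing stop: treat as continuing.
- Keep the closing exclusion sentence.

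The cost is a few lines of SAP text and a small change to the comparison operators in the program. The downside is that a few medicines that stopped just before first dose, or started just after last dose in the same month or year, will be counted. SAP 7.1.5.2 already accepts that trade for adverse events.
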